1. LIST OF ABBREVIATIONS AND ACRONYMS

A list of abbreviations used in the SAP

Term/Abbreviation	Definition
AE	Adverse Event
ART	Anti-Retroviral Therapy
COVID-19	Coronavirus disease 2019
DAIDS	Division of AIDS
DBS	Dried Blood Spot
FDA	Food and Drug Administration
GLM	Generalized Linear Model
HAV	Hepatitis A
HBV	Hepatitis B
HCV	Hepatitis C
HIV	Human Immunodeficiency Virus
HPTN	HIV Prevention Trials Network
mL	Milli-Liter
MOUD	Medication for Opioid Use Disorder
ODU	Opioid Use Disorder
PrEP	Pre-Exposure Prophylaxis
PWID	Persons Who Inject Drugs
RNA	Ribonucleic Acid
RSC	Radiation Safety Committee
SAE	Severe Adverse Event
SAP	Statistical Analysis Plan
SARS-CoV-2	Severe Acute Respiratory Syndrome Coronavirus 2
SMC	Safety Monitoring Committee
SSP	Study Specific Procedures
STI	Sexually Transmitted Infection
VL	Viral Load

2. INTRODUCTION

This statistical analysis plan (SAP) details the final analyses and statistical procedures that address the study objectives specified in Version 2.0 of Protocol HPTN 094: INTEGRRA: A Vanguard Study of Health Service Delivery in a Mobile Health Delivery Unit to Link Persons who Inject Drugs to Integrated Care and Prevention for Addiction, HIV, HCV and Primary Care. New versions of the SAP will be issued to document updates and changes in the plan.

2.1 General Design Considerations

The following is a protocol summary of the study:

Protocol title:	INTEGRRA: A Vanguard Study of Health Service Delivery in a Mobile Health Delivery Unit to Link Persons who Inject Drugs to Integrated Care and Prevention for Addiction, HIV, HCV, and Primary Care
IND Sponsor:	DAIDS
Protocol Chair(s):	[name]; [name]
Sample Size:	A total of 450 participants allotted in a 1:1 ratio to intervention and active control arms, with targets of a minimum 25% women and 25% participants under 30 years of age, and 10% people living with HIV at enrollment.
Study Population:	People living with and without HIV and who inject drugs, have OUD, and are not receiving MOUD
Study Sites:	Five urban sites in the United States (US) with substantial populations of PWID with OUD. The locations are as follows: Houston, TX; Los Angeles, CA; Bronx, NY; Philadelphia, PA; Washington, DC
Study Design:	A two-arm, individually randomized, controlled, open label study
Study Duration:	Approximately three and a half years with a possibility of extension, with individual participants on study for approximately 52 weeks (26 weeks receiving the intervention or peer navigation and then an evaluation for durability of effect at the end of 52 weeks).
Study Products:	Mobile health delivery unit ("mobile unit") to deliver "one stop" integrated health services – particularly medication for opioid use disorder (MOUD) and medication for HIV treatment and prevention – to people who inject drugs (PWID) with opioid use disorder (OUD). VS Health services available at community-based agencies
Study Regimen:	All potential study participants will provide biological samples and self-reported data via interview in the mobile unit at Screening and Enrollment Visits. Samples will be tested for HIV, hepatitis A (HAV), B (HBV) and C (HCV) and sexually transmitted infections (STIs). At the Enrollment Visit, participants who meet all inclusion and no exclusion criteria will be randomized to the intervention or active control arm and will receive harm reduction services and empiric treatment for STIs if symptomatic. Participants will also be assessed for COVID-19 at study visits; participants with suspected COVID-19 or recent

exposure will be referred for further evaluation, care and/or treatment, as available.

Intervention Arm: Participants in the intervention arm will be provided integrated health services delivered in the mobile unit and peer navigation for 26 weeks.

The integrated health services in the mobile unit will include:

MOUD and harm reduction services for OUD

HIV testing

HIV treatment for people living with HIV not already in care

PrEP for people without HIV

Testing and referral for vaccination or treatment for HAV and HBV

Testing and referral for treatment for HCV

STI testing and treatment

Primary care

Harm reduction services

Peer navigation in the intervention arm will coordinate and facilitate integrated care in the mobile unit through 26 weeks. As participants become established in care, navigation will help transition participants to community-based services by 26 weeks after randomization.

Active Control Arm: Participants in the active control arm will be provided 26 weeks of peer navigation to connect them to health services available at community-based agencies.

All participants (both arms) will have study visits at 26 and 52 weeks for evaluation of study endpoints.

2.2 Study Objectives and Endpoints

Objectives:

Primary:

To evaluate whether 26 weeks of “one stop” integrated health services delivered in a mobile unit, supported by peer navigation, improves use of MOUD and increases use of PrEP, as measured at 26 weeks among people without HIV, when compared to 26 weeks of peer navigation to similar health services available at community-based agencies.

Secondary:

- 1) To evaluate whether 26 weeks of “one stop” integrated health services delivered in a mobile unit, supported by peer navigation, compared to 26 weeks of peer navigation to similar health services available at community-based agencies:
 - a) improves use of MOUD at 52 weeks
 - b) increases rates of viral suppression among people living with HIV at 26 and 52 weeks
 - c) increases use of PrEP among people without HIV at 26 and 52 weeks
 - d) decreases opioid and polysubstance use at 26 and 52 weeks
 - e) decreases prevalence of bacterial STIs at 26 and 52 weeks
 - f) decreases fatal and non-fatal overdose events by 26 and 52 weeks
 - g) increases the proportion of participants with undetectable HCV RNA at 26 and 52 weeks among those with chronic HCV infection at enrollment

- h) decreases HCV incidence at 52 weeks, for those who are HCV negative at enrollment
- 2) To evaluate whether 26 weeks of “one stop” integrated health services delivered in a mobile unit, supported by peer navigation, increases MOUD use, viral suppression, and PrEP use at 26 and 52 weeks compared to Enrollment
- 3) To evaluate whether 26 weeks of peer navigation to similar health services available at community-based agencies increases MOUD use, viral suppression, and PrEP use at 26 and 52 weeks compared to Enrollment
- 4) To document the prevalence of seropositivity for SARS-CoV-2 at baseline, 26 and 52 weeks
- 5) To document the impact of the COVID-19 epidemic on participants’ experiences of seeking, obtaining and/or maintaining health services, housing, food security and drugs
- 6) To evaluate implementation of “one-stop” integrated health services using a mobile unit, supported by peer navigation, across study sites to identify mechanisms at multiple levels to:
 - a) Guide real-time improvements and refinements in the conduct of the study to ensure primary and secondary outcomes are met with fidelity
 - b) Examine the quality and process of services delivered in each study arm, particularly as these affect primary and secondary outcomes
 - c) Develop evidence-based guidance for policymakers on the uptake and implementation of integrated health services using peer navigation and mobile health units in urban US regions to address HIV prevention in PWID
 - d) Identify factors that enhance or impede the delivery of integrated health services using a mobile unit, supported by peer navigation, on primary and secondary outcomes, including responding to the impact of COVID-19 on service delivery
- 7) To use mathematical modeling methods to:
 - a) Estimate the effect of integrated health services delivered in a mobile unit, supported by peer navigation, on reducing HIV incidence in PWID and their sexual and injection partners
 - b) Estimate the cost-effectiveness of the integrated health services provided in a mobile unit and supported by peer navigation

Process:

For participants in the intervention arm, assess:

1. Time to provide MOUD treatment, ART (among those who are living with HIV and not on ART at Enrollment) and PrEP (among those who are without HIV at Enrollment)
2. The proportion of participants linked to community based MOUD, ART and PrEP services at 26 weeks

Exploratory Objectives:

Stored samples may be used to analyze HIV subtypes/strains, HIV drug resistance, and the duration of HIV infection. Phylogenetic methods may be used to evaluate behavioral, demographic, and clinical factors associated with viral clusters and transmission dynamics. Stored samples may also be used to characterize HCV strains and the relationship between HIV and HCV infections, and to explore issues related to COVID-19.

Endpoints:***Primary:***

Consistent with the primary study objective to evaluate whether the intervention improves use of MOUD and increases use of PrEP, as measured at 26 weeks among people without HIV, the following endpoints will be assessed:

1. Documented current use of MOUD. At the Week 26 visit:
 - a) Alive
 - b) Retained
 - c) Biological evidence of MOUD (any detectable Methadone or Buprenorphine)
 - d) A MOUD prescription current at the week 26 visit or proof of current receipt of MOUD from a clinic that does not provide individual MOUD prescriptions (e.g., methadone clinics)
2. Among participants who were without HIV at enrollment: alive, retained, without HIV, with detectable PrEP drugs (Truvada or Descovy in dried blood spot (DBS) samples, or Cabotegravir in plasma samples at the week 26 visit

Secondary:

1. To evaluate whether “one stop” integrated health services delivered in a mobile unit, supported by peer navigation, compared to peer navigation to similar health services available at community-based agencies, the following endpoint(s) will be assessed:
 - a. The intervention improves use of MOUD at 52 weeks
 - Documented current use of MOUD: alive, retained, with biological evidence of MOUD (any detectable medications) at the week 52 visit and a MOUD prescription current at 52 weeks after enrollment or proof of current receipt of MOUD from a clinic that does not provide individual MOUD prescriptions (e.g., methadone clinics) at the week 52 visit
 - Documented use of MOUD during the study: a MOUD prescription documented during the 52 weeks of study follow-up or proof of current receipt of MOUD from a clinic that does not provide individual MOUD prescriptions (e.g., methadone clinics) during the 52 weeks of study follow-up
 - b. The intervention increases rates of viral suppression among people living with HIV at 26 and 52 weeks
 - Among participants living with HIV at enrollment: alive, retained, and virally suppressed (VL <200 copies/mL) at the week 26 and week 52 visits, separately.
 - c. The intervention increases use of PrEP among people without HIV at 26 and 52 weeks
 - Among participants without HIV at enrollment: alive, retained, HIV negative, with detectable PrEP drugs in DBS at the week 52 visit
 - Among participants without HIV at enrollment: alive, retained, HIV negative, with protective levels of PrEP drugs in DBS samples at the week 26 and 52 visits
 - d. The intervention decreases opioid and polysubstance use at 26 and 52 weeks
 - Alive, retained, and no opioids (natural or synthetic), stimulants (methamphetamine, cocaine) or benzodiazepines detected in urine samples at week 26 and 52 visits
 - e. The intervention decreases prevalence of bacterial STIs at 26 and 52 weeks
 - Alive, retained and no evidence of gonorrhea, chlamydia, or new or recurrent syphilis infection detected at the week 26 and 52 visits

- f. The intervention reduces the rate of fatal and non-fatal overdose events by 26 and 52 weeks,
 - Death, with overdose as cause
 - Self-report of non-fatal overdose, collected at week 26 and 52 visits
 - g. The intervention increases the proportion of participants with undetectable HCV RNA among those with chronic HCV infection at enrollment
 - Undetectable HCV RNA at the week 26 and 52 visits among participants with chronic HCV at enrollment
 - h. The intervention reduces HCV incidence
 - HCV antibody positive at the week 52 visit among participants who are HCV antibody negative at enrollment
2. To evaluate whether 26 weeks of “one stop” integrated health services delivered in a mobile health delivery unit, supported by peer navigation, increases MOUD use, viral suppression, and PrEP use at 26 and 52 weeks compared to enrollment, the following endpoint(s) will be assessed:
 - In the intervention arm, change over time in the use of MOUD during the study, comparing documented use of MOUD (biological evidence of MOUD - any detectable medications - and a current MOUD prescription or proof of current receipt of MOUD from a clinic that does not provide individual MOUD prescriptions (e.g., methadone clinics)) at 26 and 52 weeks to documented use of MOUD at enrollment. MOUD use is assumed to be zero at enrollment due to study exclusion criteria. Follow-up endpoints will be defined as alive, retained, and having documented MOUD use.
 - Among participants living with HIV at enrollment: change over time in the proportion of people with viral suppression (VL<200 copies/mL), comparing 26 and 52 weeks to enrollment. Follow-up endpoints will be defined as alive, retained, and virally suppressed.
 - Among participants who were without HIV at enrollment: change over time in the proportion of people with detectable PrEP drugs in DBS at 26 and 52 weeks compared to enrollment. Follow-up endpoints will be defined as alive, retained, and having detectable PrEP.
3. To evaluate whether 26 weeks of peer navigation to similar health services available at community-based agencies increases MOUD use, viral suppression, and PrEP use at 26 and 52 weeks compared to enrollment, the following endpoint(s) will be assessed:
 - In the active control arm, change over time in the use of MOUD during the study, comparing documented use of MOUD (biological evidence of MOUD - any detectable medications - and a current MOUD prescription or proof of current receipt of MOUD from a clinic that does not provide individual MOUD prescriptions (e.g., methadone clinics)) at 26 and 52 weeks to documented MOUD use at enrollment. MOUD use is assumed to be zero at enrollment due to study exclusion criteria. Follow-up endpoints will be defined as alive, retained, and having documented MOUD use.
 - In the active control arm among participants living with HIV at enrollment: change over time in the proportion of people with viral suppression (VL<200 copies/mL), comparing 26 and 52 weeks to enrollment. Follow-up endpoints will be defined as alive, retained, and virally suppressed.
 - In the active control arm among participants who were without HIV at enrollment: change over time in the proportion of people with detectable PrEP drugs in DBS at 26

and 52 weeks compared to enrollment. Follow-up endpoints will be defined as alive, retained, and having detectable PrEP.

4. To assess the prevalence of SARS-CoV-2 seropositivity at baseline, 26 and 52 weeks, the following endpoint will be assessed:
 - Laboratory evidence of antibodies to SARS-CoV-2

The rest of the endpoints will be handled separately in a different SAP or will be added later.

2.3 Randomization

Random treatment-arm allocation will occur at a 1:1 ratio, stratified by study site and by HIV status. Permuted-block randomization will be used to assure balanced groups within each study site and HIV-status subgroup with 30 blocks per site/HIV-status stratum. A list of size 240 [$10 \times (6+8+10)$] would allow each site more than enough randomization slots in case a site is called upon to enroll greater than the projected sample size (approx. $n=80$ HIV negative participants and approx. $n=10$ HIV positive participants per site), or in case of dropouts or randomization errors.

2.4 Blinding

This study is unblinded.

2.5 Sample Size and Power

Sample sizes are chosen to provide sufficient power for both the HIV-related and MOUD-related primary outcomes. By computing sample sizes based on each individual outcome separately and choosing the largest sample size needed for either outcome, high power is achieved for both individual outcomes. Prior work in PWID populations suggests that uptake of MOUD, ART, and PrEP in the control condition will likely be modest;^{1,2} we anticipate 25% uptake of MOUD, 42.5% achieving viral suppression, and 5% uptake of PrEP in the control arm.

Sample sizes are computed to provide 90% power to detect a fifteen-percentage point difference in the proportion of participants achieving success, assuming a 5% type-I error rate (two-sided). A sample of 400 participants is needed to detect a 15-point difference in MOUD use (25% vs. 40%) between the active control and intervention arm at 26 weeks. Approximately 216 people without HIV would be needed to see a 15-point difference in PrEP uptake (5% vs. 20%). To cover both HIV and MOUD outcomes, 400 people without HIV will be needed. Approximately 10% of the study population is expected to be living with HIV – insufficient to accommodate a fully powered subgroup - but because this subgroup is expected to have very different rates of HIV-related success than the people without HIV subgroup, it will be important to analyze these participants separately. To assure 400 people without HIV, the target sample size will be augmented by 50 for a combined total of 450 participants, where 40-50 of those are expected to be people living with HIV.

2.6 Accrual and Retention

The study cohort ($n=450$) will be enrolled over the course of approximately 2.5 years and followed for 52 weeks each. This corresponds to a rate of approximately 15 new enrollees per month, or approximately 3 new enrollees per month at each of the five sites.

3. GENERAL DATA ANALYSIS CONSIDERATIONS

3.1 Analysis Set(s)

- **Intent to Treat (ITT):**
All participants enrolled, excluding those who were inappropriately enrolled.
- **Safety:**
There is no formal safety analysis in this study, however, serious adverse events (SAE) will be monitored for all randomized participants.

3.2 Statistical Analysis Issues

- **Missing Data:**
In anticipation of the potential for missing data in this unstable study population, a missing-data strategy has been built into the primary endpoints. A positive result for each endpoint is defined as being “alive, retained,” and meeting the MOUD, ART, or PrEP criteria at 26 weeks from enrollment. If the 26-week visit is missing for any individual, that individual is “not retained” at 26 weeks, and the 26-week result for that person will be considered “negative”.

Secondary endpoints are defined similarly. If missing data rates are higher than anticipated (over 15%) for primary or secondary endpoints, sensitivity analyses will be conducted to assess the impact of assuming missed visits represent negative outcomes.
- **Missing Start and Stop Dates:**
Start date:
 - If start date is completely missing, start date will not be imputed.
 - If year is present and month and day are missing, then set month and day to January 1 or date of enrollment whichever is later.
 - If year and day are present and month is missing, the set month to January or date of enrollment whichever is later.
 - If year and month are present and day is missing, set day to the 1st day of month or date of enrollment whichever is later.Stop date:
 - If end date is completely missing, end date will not be imputed.
 - If year is present and month and day are missing, then set month and day to December 31st or date of termination whichever is earlier.
 - If year and day are present and month is missing, set month to December or date of termination whichever is earlier.
 - If year and month are present and day is missing, set day to the last day of month.
- **Out of window visits:**
For each required study visit, there is an allowable visit window specifying on which study days (post-enrollment) the visit is “allowed” to be completed. The allowable visit windows are contiguous between week 26 and week 52 and do not overlap. Within each allowable visit window, there is a target visit window and study visits should ideally be conducted within this window. Further details about visit windows are defined at section 6.8 of the Protocol V2.0.

All data will be tabulated per the evaluation visit as recorded on the CRF even if the assessment is outside of the visit window. In data listings, actual visit dates will be presented alongside nominal visit types.

4. INTERIM ANALYSIS AND DATA MONITORING COMMITTEE

No interim analyses are planned.

HPTN SMC oversight is planned for this study. The SMC will conduct interim reviews of study progress, including rates of participant accrual, visit retention, completion of primary and secondary endpoint collection, and, in a closed report, endpoint and safety data by arm. The frequency and content of SMC reviews will be determined prior to the start of the study and outlined in the SSP Manual but will occur at least once per calendar year.

5. GENERAL ANALYSIS METHODS

Participants characteristics at baseline will include the number of subjects with non-missing value (n), plus frequency and percentage for the categorical variables; and mean, median, standard deviation (SD), minimum (min), and maximum (max) for the continuous variables. Baseline is defined as Enrollment visit, except for data collected at screening and not at enrollment visit. For example, opioids data collected at screening visit will be considered as baseline data.

Any deviations from this statistical plan will be described in the final report. Primary and secondary outcomes will be limited to data collected within the allowable visit window for the week 26 and week 52 visits, respectively.

For all outcomes below, “retained” at 26 weeks is defined as having completed the 26-week visit within the allowable window of 126-308 days from enrollment, and “retained” at 52 weeks is defined as having completed the 52-week visit within the allowable window of 309-449 days from enrollment.

[figure not shown]
For MOUD outcomes, biological detection of Buprenorphine (or Norbuprenorphine or Buprenorphine Glucuronide) or Methadone (or EDDP) will be performed via laboratory analysis of plasma and urine samples. Detectable MOUD is defined as a value above the lower limit of quantitation (LLOQ) for any of the medications or metabolites mentioned above, in either plasma or urine.

For PrEP outcomes, the PrEP regimen tested (Truvada or Descovy in DBS, or CAB-LA in plasma) is determined based upon reported PrEP use. If there is no reported PrEP usage, the default regimen is Truvada. Detectable PrEP is defined as a value above the lower limit of quantitation (LLOQ) for the PrEP regimen tested.

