10. SECONDARY ENDPOINTS

1. **To evaluate whether “one stop” integrated health services delivered in a mobile unit, supported by peer navigation, compared to peer navigation to similar health services available at community-based agencies, the following endpoint(s) will be assessed:**
 - a) Improves use of MOUD at 52 weeks compared to the active control condition

Outcomes:

- Documented current use of MOUD: alive, retained, with biological evidence of MOUD (as defined above) at the week 52 visit and a MOUD prescription current at 52 weeks after enrollment or proof of current receipt of MOUD from a clinic that does not provide individual MOUD prescriptions (e.g., methadone clinics) at the week 52 visit
- Documented use of MOUD during the study: a MOUD prescription documented during the 52 weeks of study follow-up or proof of current receipt of MOUD from a clinic that does not provide individual MOUD prescriptions (e.g., methadone clinics) during the 52 weeks of study follow-up

These outcomes will be modeled and summarized using the same strategy as specified for the primary outcome in section 8 above.

- b) Increases rates of viral suppression among people enrolled living with HIV, at 26 and 52 weeks

Outcome:

- Among participants living with HIV at enrollment: alive, retained, and virally suppressed (VL <200 copies/mL) at the week 26 and 52 visits, separately.

The proportion of participants achieving the viral suppression outcome will be computed and presented by arm and within site by arm, along with exact Clopper-Pearson 95% confidence intervals using F-quantiles based on the Binomial distribution. No statistical comparisons between treatment arms will be made.

- c) The intervention increases use of PrEP among people without HIV at 26 and 52 weeks

Outcome:

- Among participants without HIV at enrollment: alive, retained, HIV negative, with detectable PrEP drugs in DBS at the week 52 visit
- Among participants without HIV at enrollment: alive, retained, HIV negative, with protective levels of PrEP drugs in DBS samples at the week 26 and 52 visits

A protective level of oral PrEP³ is defined as:

TFV-DP concentrations ≥ 800 fmol/punch in DBS among those tested for Truvada (TDF-FTC)

TFV-DP concentrations ≥ 950 fmol/punch in DBS among those tested for Descovy (TAF-FTC)

A protective level of long-acting PrEP (Cabotegravir) is defined as plasma concentrations above the four times the PA-IC₉₀ of 166 ng/mL – that is, above 664 ng/mL.

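### The week-26 primary PrEP endpoint is scored only on the regimen chosen from reported use, so unreported cabotegravir counts as failure where SAP section 2.2 counts it as success

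*SAP*

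**What the plan says.** Section 2.2 of the SAP (primary endpoint 2) defines PrEP success, for participants without HIV at enrollment, by detection in the sample: "with detectable PrEP drugs (Truvada or Descovy in dried blood spot (DBS) samples, or Cabotegravir in plasma samples at the week 26 visit". It sets no condition on what the participant or anyone else reported.

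Section 8 refers to section 5 for the meaning of detectable PrEP. Section 5 gives three linked rules:

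- Choice of assay: "the PrEP regimen tested (Truvada or Descovy in DBS, or CAB-LA in plasma) is determined based upon reported PrEP use".
- Default: "If there is no reported PrEP usage, the default regimen is Truvada".
- Scoring: "Detectable PrEP is defined as a value above the lower limit of quantitation (LLOQ) for the PrEP regimen tested".

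Section 5 does not say whose report counts (the participant, a prescriber or a clinic record), or what is done when more than one regimen is reported. The change history shows that version 2.0 brought in the wording on PrEP regimen testing, so this is current and deliberate text.

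The MOUD rule in the same section works differently. A participant is positive on a value above LLOQ "for any of the medications or metabolites mentioned above, in either plasma or urine", whatever was reported.

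Section 10 (item 1c) shows what is measured for each regimen. For Truvada the protective level is "TFV-DP concentrations ≥ 800 fmol/punch in DBS among those tested for Truvada (TDF-FTC"). For Descovy it is "TFV-DP concentrations ≥ 950 fmol/punch in DBS among those tested for Descovy (TAF-FTC"). For the injectable: "A protective level of long-acting PrEP (Cabotegravir) is defined as plasma concentrations" above 664 ng/mL. The two oral regimens thus share analyte and matrix; cabotegravir shares neither.

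Section 2.4 states that there is no blinding. The only sensitivity analysis in section 3.2 concerns missed visits, when missing data exceed 15%.

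**The concern.** The endpoint is meant to be an objective laboratory measure. Under section 5, whether a drug present in the sample can be found depends on information from outside the laboratory. A person can meet the definition in section 2.2 and be a failure under section 5, only because no report led to the plasma assay.

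This touches one of the two primary endpoints. If such misses occur equally in both arms, the estimated difference shrinks. If they occur more in one arm, the difference is biased, and under no true effect the false-positive rate exceeds 5%. In an unblinded trial where one arm can receive PrEP in the mobile unit and the other is navigated to outside agencies, what is known about the regimen could differ by arm. No planned table or analysis would show whether it did.

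**Working it through.** **Step 1: the two definitions side by side.** Each row assumes a retained participant who is HIV negative at week 26 and has the named drug above LLOQ.

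| Drug taken | Reported | Assay under section 5 | Section 2.2 | Section 5 |
|---|---|---|---|---|
| Cabotegravir | Cabotegravir | plasma | success | success |
| Cabotegravir | nothing | DBS, as Truvada | success | negative, unless TFV-DP is also present |
| Cabotegravir | oral regimen only | DBS | success | negative, unless TFV-DP is also present |
| Descovy | nothing | DBS, as Truvada | success | normally success (TFV-DP found) |
| Truvada | nothing | DBS, as Truvada | success | success |

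The definitions part only in the second and third rows. The Descovy row would change only if the LLOQ differed by regimen, which the SAP does not state. On the secondary protective-level outcome, the same Descovy user with TFV-DP of 800-949 fmol/punch is called protected under the Truvada default (cut-off 800) and would not be under the Descovy rule (cut-off 950).

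**Step 2: the plan's own PrEP figure.** Inputs from section 2.5: 5% vs 20%, 90% power, two-sided 5%, stated total about 216. The SAP names no method. Normal-approximation formulas give 202 (pooled variance), 194 (unpooled) and 228 (continuity-corrected). Exact power for Fisher's test is 89.6% at 104 per arm, 90.2% at 106 (total 212) and 90.9% at 108 (total 216). The stated figure is reproduced on that basis and is not in dispute.

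**Step 3: power at the planned size.** Section 2.5 plans 400 people without HIV, so 200 per arm at 1:1. With s0 = √(2·p̄(1−p̄)/n) and s1 = √([p1(1−p1) + p2(1−p2)]/n):

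- p̄ = 0.125, s0 = √(2 × 0.125 × 0.875/200) = 0.0331
- s1 = √((0.0475 + 0.16)/200) = 0.0322
- power = Φ((0.15 − 1.96 × s0)/s1) = Φ(2.64) = 99.6%

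Sample size is therefore not the weak point.

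**Step 4: weight of one missed user.** Expected control successes: 0.05 × 200 = 10. One miss is 1/200 = 0.5 percentage points. If, as an assumption, 1 to 3 of the 10 were missed, the observed control rate would be 9/200 = 4.5% to 7/200 = 3.5%.

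**Step 5: range.** Let m be the share of true PrEP users scored negative because their drug was not assayed. The SAP gives no value for m; 10%, 30% and 50% are assumptions. True rates are taken as 5% and 20%, with 200 per arm.

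| Where the misses fall | Observed difference | m = 10% | m = 30% | m = 50% |
|---|---|---|---|---|
| Both arms equally | 15(1−m) | 13.5 points (power 99.1%) | 10.5 (96.3%) | 7.5 (87.5%) |
| Control only | 20 − 5(1−m) | 15.5 points | 16.5 | 17.5 |
| Intervention only | 20(1−m) − 5 | 13.0 points (power 98.5%) | 9.0 (86.9%) | 5.0 (47.5%) |

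With no true difference and misses in the control arm only, the chance of a significant result is 5.6%, 11.5% and 26.0% when true use is 5% in both arms, and 8.0%, 35.8% and 80.2% when it is 20%. The formula is symmetric, so misses in the intervention arm only give the same rates, with the spurious effect reversed.

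**The case against.** **Section 5 only makes section 2.2 operational.** Section 8 does refer to section 5, and version 2.0 added the rule on purpose. That settles which text governs. It does not remove the disagreement: the operational rule scores as failures some people whom the stated endpoint counts as successes.

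**Reported need not mean self-reported.** This stands. The SAP writes self-report where it means it, as for non-fatal overdose. If records or staff knowledge already count, fewer users are missed. But the source is left open, and it may differ between arms unless it is fixed.

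**A reader might infer that the rule favours the intervention**, because mobile-unit staff know what they prescribed. The SAP does not support that. Controls also have 26 weeks of peer navigation, which gives study staff a route to regimen information. Intervention participants are to move to community services by week 26, and the visit window runs to day 308, so their PrEP too may come from outside. Step 5 shows that bias in either direction is possible.

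**A reader might also infer that unreported Descovy users are lost from the primary endpoint.** They normally are not, because TFV-DP in DBS is the measure for both oral regimens.

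**The sizes are assumed.** They are. The SAP gives no cabotegravir uptake and no under-reporting rate. At 1 to 3 missed controls the shift is 0.5 to 1.5 points on a 15-point difference with ample power.

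**Conclusion.** The point holds for cabotegravir on the primary endpoint. Section 5 scores as negative a cabotegravir user who reports no PrEP, or only an oral regimen (unless TFV-DP is also present), and section 2.2 counts that person as a success. For Descovy it holds only for the secondary protective-level outcome, in the band 800-949 fmol/punch, and rests on the same cut-offs continuing to apply by regimen tested.

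The direction and size of any bias are unknown. The one figure that follows from the SAP's own assumptions is 0.5 percentage points per missed control, against 10 expected control successes. All larger figures depend on an assumed miss share and on how it splits between arms. The defect lies in the endpoint rule and its lack of any check by arm; it is not evidence that the PrEP result will be inflated.

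**What to change.** In section 5:

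1. State the source of reported use, and apply one selection rule in both arms: participant report, or any available prescription, dispensing or injection record.
2. Assay every regimen so identified, and count success if any is above LLOQ, so that section 5 agrees with section 2.2.
3. Tabulate by arm the regimen tested and the number tested by default.
4. Where plasma drawn for MOUD testing remains, add a sensitivity analysis that runs the cabotegravir assay for default-tested participants, in both arms alike.
5. For default-tested participants, report the protective-level outcome under both the 800 and the 950 fmol/punch cut-offs. Using either alone would misclassify users of the other oral regimen in that band.

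A participant who reports an oral regimen and has no cabotegravir record would still not be tested in plasma. The table in item 3 bounds how many could be in that position.

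The cost is a change of SAP wording, a limited number of further assays on plasma in hand, and a few tables. No new visits or participants are needed. Two limits apply: the SAP requires prescription or receipt evidence for MOUD but not for PrEP, so PrEP records can be used only where they exist; and it does not show how much plasma will be left after MOUD testing.
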